3.7.4 End of Trial

The end of trial date is defined as the last date of contact or the date of final contact attempt from the post-treatment follow-up visit for the last subject completing or withdrawing from the trial.

Protocol 031-201-00301

3.8 Stopping Rules, Withdrawal Criteria, and Procedures

3.8.1 Entire Trial

If the sponsor terminates or suspends the trial for any reason, prompt notification will be given to investigators, IRB, and regulatory authorities in accordance with regulatory requirements.

3.8.2 Individual Site

Individual trial site participation may be discontinued by the sponsor, the investigator, or the IRB if judged to be necessary for medical, safety, regulatory, ethical or other reasons consistent with applicable laws, regulations, and GCP. The investigator will notify the sponsor promptly if the trial is terminated by the investigator or the IRB at the site.

3.8.3 Individual Subject Discontinuation

3.8.3.1 Treatment Discontinuation

After enrollment, a subject may stop Abilify MyCite treatment permanently for a variety of reasons. Treatment discontinuations may be initiated by a subject who is not satisfied with treatment or may become medically necessary due to AEs, device-related nonserious AEs, required treatment with a disallowed medication or therapy, or other issues, as determined by the investigator. For subjects who elect to discontinue early for any reason, the sponsor would like to follow the subject for the total trial duration to track healthcare utilization with and without use of Abilify MyCite.

By Day 14 of the trial, if it is the opinion of the investigator that it is not appropriate for a subject to continue using Abilify MyCite, then the subject may be discontinued from trial participation but will be followed on oral atypical antipsychotic medication through the Month 6/ET visit.

If any subject discontinues the trial early, every effort should be made to complete the Month 6/ET evaluations (see [Table 3.7-1](#)) at that visit. All subjects (completers and early withdrawals) will be contacted to monitor for safety events via telephone or investigator visit at 1 month (\pm 3 days) after the Month 6/ET visit.

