During the assessment period, subjects will visit the investigator for clinical evaluations at baseline (Day 1), Month 3, and Month 6/early termination (ET). Monthly assessments will follow a 28-day schedule, and at each visit and at any unscheduled visits, the subject's clinical status will be evaluated. All hospitalizations and all interventions (psychiatric only as well as pharmacy cost of all medications) will be recorded, in addition to all other assessments outlined in this protocol. The primary endpoint will be assessed at Month 3. The final trial visit will be on Month 6/ET and will be followed by a 30-day (\pm 3 day) safety follow-up period for subjects continuing on Abilify MyCite. For subjects completing Months 4 to 6 on standard of care, a 30-day safety follow-up period is not required. Subjects will also visit the clinic for medication dispensing and accountability at Months 1, 2, 4, and 5. Any treatment changes, including reason for the change, will be recorded in the electronic case report form (eCRF).

Evaluation of safety and tolerability of Abilify MyCite as assessed by frequency and severity of the AEs to be collected in this trial, ie, serious AEs (SAEs), device-related nonserious AEs, potential hepatotoxicity cases, and pregnancies.

Subject use of the Abilify MyCite system can be monitored by their respective investigators, who are suggested to review the physician dashboard data at a minimum of every 2 weeks and make changes to current treatment plan and therapy at their discretion. The investigators may request that a subject return to the site for unscheduled visits as deemed appropriate. In the event of an unscheduled visit, review of the investigator dashboard and safety events will be collected.

Protocol 031-201-00301

Safety Follow-up

All subjects who complete or withdraw from the trial while on Abilify MyCite (unless they have withdrawn their consent for participation in the trial) will receive a telephone call for safety follow-up at 30 days (\pm 3 days) after the last trial visit.

This telephone contact will be made to assess if there were any AEs experienced since the last trial visit. In addition, the subject will be asked about any new medications or changes in existing medications and the information will be documented. The trial design is presented in [Figure 3.1-1](#).

Protocol 031-201-00301

[figure not shown]

Figure 3.1-1 Trial Design Schematic

Note: Monthly assessments will follow a 28-day schedule.

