3.7 Trial Procedures

The duration of this trial from first subject enrolled to first subject completed is estimated to be up to approximately 8.5 months including a 45-day screening period and a 6-month prospective phase that includes a required 3 months (Months 1 to 3) of Abilify MyCite

Protocol 031-201-00301

treatment. This will be followed, at investigator discretion, to either change to standard-of-care antipsychotic treatment (eg, oral or LAI) or remain on Abilify MyCite for the second 3-month period (Months 4 to 6), during the prospective phase. The final trial visit will be on Month 6/ET and will be followed by a 30-day (\pm 3 day) safety follow-up period for subjects continuing on Abilify MyCite. For subjects completing Months 4 to 6 on standard of care, a 30-day safety follow-up period is not required. Total length of participation in the trial will vary depending on the screening duration and if the subjects remain on Abilify MyCite treatment.

At the screening visit, informed consent will be obtained before any trial-related assessments or procedures are performed. Initiation of the Abilify MyCite treatment will commence at the baseline visit (Day 1) for the subjects who meet all applicable eligibility criteria (Section 3.4), based on a series of assessments conducted at the screening visit. The first dose of Abilify MyCite is to be taken at the baseline (Day 1) visit (in the clinic) during onboarding, unless they have already taken their daily dose. Subjects should not take their oral standard-of-care medication that morning before the baseline visit.

During screening visit, the investigator will provide training on the correct use and required procedures associated with Abilify MyCite. The subject will be provided with patches, aripiprazole tablet embedded with an IEM sensor (Abilify MyCite) product, other supplies, and instructions on the procedures to be followed over the coming weeks.

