Subjects will be monitored on the technology by the investigators, who can review the physician dashboard data and make changes to current treatment plan and therapy at their discretion. The investigators may request that a subject return to the site for unscheduled visits as deemed appropriate. In the event of an unscheduled visit, data collected will be at the investigator discretion per allowed data collection points noted in the schedule of assessments (Table 3.7-1). By Day 14 of the trial, if it is the opinion of the investigator that it is not appropriate for a subject to continue using Abilify MyCite, then the subject may be discontinued from trial participation but will be followed on oral atypical antipsychotic medication through the Month 6/ET visit.

Subjects will also visit the clinic for dispensing patches, Abilify MyCite product, and other supplies at Months 1, 2, 4, and 5. Any treatment changes, including reason for the change, will be recorded in the eCRF. Additionally, clinical evaluations will occur at Month 3 visit.

At the Month 6/ET visit, designated assessments and procedures will be conducted. The Month 6/ET visit marks the end of the assessment period. The subject will stop taking

Protocol 031-201-00301

Abilify MyCite product and will restart his/her standard-of-care treatment (routine follow-up from care teams). All trial materials will be returned to the trial site.

For subjects continuing on Abilify MyCite, a follow-up telephone contact will be made 30 days (\pm 3 days) after the last dose of aripiprazole tablet embedded with an IEM sensor (Abilify MyCite) product (for subjects who withdraw early and for those who complete the trial). The Month 6/ET visit will serve as the final safety visit for subjects who complete the study on standard-of-care treatment.

Trial assessment time points are summarized in [Table 3.7-1](#).

Protocol 031-201-00301

Table 3.7-1 Schedule of Assessments										
Assessments	Screening Days -45 to -1	Prospective Phase (Day 1 to Month 6/ET)^a							Follow -Up^b	Notes
		Abilify MyCite treatment required (Months 1 to 3)			Abilify MyCite or PRN oral atypical antipsychotic treatment (Months 4 to 6)					
		Baseline	Month 1	Month 2	Month 3	Month 4	Month 5	Month 6/ET	Month 7	
		Day 1	- 3/+ 2 days			- 3/+ 2 days			± 3 days	
Record retrospective hospitalization and intervention data per protocol	X ^c									
Informed consent	X									Section 3.4.1
Inclusion/exclusion criteria	X									Section 3.4

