Demographic information	X									
Psychiatric history	X									
Urine pregnancy test (WOCBP) ^d	X	X								Section 3.7.3.2
Confirmation of diagnosis of schizophrenia by DSM-5	X									
C-SSRS (Baseline/Screening Version)	X									Section 3.7.3.5
C-SSRS (Since Last Visit Version)		X			X			X		Section 3.7.3.5
ECG collection	X									Section 3.7.3.4
Vital signs	X	X			X			X		Section 3.7.3.3
Adverse events	X	X			X			X	X	Section 5
Discontinue prohibited medications	X									Section 4
Smartphone verification	X									
Onsite onboarding with Abilify MyCite; subject pairs/applies patch		X								Section 3.2.2.2
Dispense aripiprazole tablet embedded with an IEM sensor (Abilify MyCite), patches, and other supplies		X	X	X	X	X ^e	X ^e			
Review Abilify MyCite dashboard data every 2 weeks		X	--X ^f --			--X ^f --			--X ^f --	

Protocol 031-201-00301

Table 3.7-1 Schedule of Assessments										
Assessments	Screening	Prospective Phase (Day 1 to Month 6/ET)^a							Follow-Up^b	Notes
		Baseline	Abilify MyCite treatment required (Months 1 to 3)			Abilify MyCite or PRN oral atypical antipsychotic treatment (Months 4 to 6)				
		Month 1	Month 2	Month 3	Month 4	Month 5	Month 6/ET	Month 7		
		Day 1	- 3/ + 2 days			- 3/ + 2 days			± 3 days	
Accountability for aripiprazole tablet embedded with an IEM sensor (Abilify MyCite), patches, and other supplies			X	X	X	X ^e	X ^e	X ^e		
Healthcare utilization record evaluation					X			X		Section 3.7.1.4
Subject usability and satisfaction scale					X			X ^g		Section 3.7.2.1.8
Follow-up phone call									X	

Protocol 031-201-00301

- ^a Monthly assessments will follow a 28-day schedule.
- ^b A follow-up phone call for subjects who conclude the study on Abilify MyCite will occur 30 days (\pm 3 days) after the Month 6/ET visit.
- ^c Retrospective hospitalization and intervention data will be collected only after trial eligibility is confirmed. This includes all psychiatric interventions (ie, hospitalizations, emergency department visits, partial hospitalization visits, intensive outpatient visits, assertive community treatment visits, outpatient visits for psychotherapy and/or medication management, etc.).
- ^d Urine pregnancy tests may be repeated if the investigator suspects that a subject is pregnant.

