3.7.1.3.5 Month 6/Early Termination Visit

Month 6/ET (- 3/ + 2 days) will be an investigator visit for the subject. In addition, Month 6/ET visit evaluations are to be completed for any subject withdrawn from the trial at any time (for any reason other than full withdrawal of the consent). At the Month 6/ET visit, the following will be performed:

- Administer the suicidality assessment (C-SSRS Since Last Visit Version; [Section 3.7.3.5](#)).
- Perform vital signs assessment ([Section 3.7.3.3](#)).
- Monitor AEs, including device-related nonserious AEs ([Section 5](#)).
- Accountability of patches and Abilify MyCite product (aripiprazole tablet embedded with an IEM sensor) supplies performed for subjects remaining on Abilify MyCite treatment. Any treatment changes, including reason for the change, will be recorded in the eCRF.
- Review Abilify MyCite dashboard data every 2 weeks for subjects remaining on Abilify MyCite treatment.

Protocol 031-201-00301

- [REDACTED]
- [REDACTED]
- [REDACTED]
- [REDACTED]
- [REDACTED]
- [REDACTED]
- Healthcare utilization record evaluation ([Section 3.7.1.4](#)).
- [REDACTED]
- [REDACTED]
- [REDACTED]
- [REDACTED]

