5.7.2 Follow-up of Serious Adverse Events and Immediately Reportable Events

This trial requires that subjects be actively monitored for SAEs and IREs up to 1 month after the last dose of Abilify MyCite is administered.

Serious AEs and nonserious IREs that are identified or ongoing at the last scheduled contact must be recorded as such on the AE eCRF page. If updated information (eg, resolved status) on SAE or IRE status becomes available after a subject's last scheduled contact (up to the last in-clinic visit for the entire trial), this must be reported to the sponsor and recorded on the AE eCRF page, according to the appropriate reporting procedures. The investigator will follow SAEs until the events are resolved, stabilized, or the subject is lost to follow-up or has died. Resolution means that the subject has returned to the baseline state of health and stabilized means that the investigator does not expect any further improvement or worsening of the subject's condition. The investigator will continue to report any significant follow-up information to the sponsor up to the point the event has resolved or stabilized, or the subject is lost to follow-up or has died.

5.7.3 Follow-up and Reporting of Serious Adverse Events and Immediately Reportable Events Occurring after Last Scheduled Contact

Any new SAEs or IREs reported to the investigator, which occur after the last scheduled contact and are determined by the investigator to be reasonably associated with the use of Abilify MyCite, should be reported to the sponsor. This may include SAEs or IREs that are captured on follow-up telephone contact or at any other time point after the defined trial period. The investigator should follow SAEs or IREs identified after the defined trial period and continue to report any significant follow-up information to the sponsor until the events are resolved or stabilized, or the subject is lost to follow-up or has died.

Protocol 031-201-00301

6 Pharmacokinetic Analysis

Not applicable, no pharmacokinetic assessments will be performed in this trial.

7 Statistical Analysis

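### The protocol gives conflicting rules on who receives the 30-day safety contact, and under the restrictive one late stoppers get less than the required month of active post-dose monitoring

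*Protocol*

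**What the plan says.** Two texts are broad:

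- Protocol Section 3.8.3.1: "All subjects (completers and early withdrawals) will be contacted to monitor for safety events via telephone or investigator visit at 1 month", with a tolerance of 3 days either side, counted from the Month 6/ET visit.
- Protocol Section 5.7.2 requires that "subjects be actively monitored for SAEs and IREs up to 1 month after the last dose of Abilify MyCite", with no exemption.

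The others are restrictive:

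- Table 3.7-1 footnote b and Section 3.7.1.5: "A follow-up phone call for subjects who conclude the study on Abilify MyCite will occur 30 days" after the Month 6/ET visit. Section 3.7.1.5 treats this call as the last planned contact.
- The synopsis, Section 3.1 and SAP Section 3.1 give the call to "All subjects who complete or withdraw from the trial while on Abilify MyCite", barring withdrawn consent.
- Section 3.7: "For subjects continuing on Abilify MyCite, a follow-up telephone contact will be made 30 days" after the last dose. It then adds: "The Month 6/ET visit will serve as the final safety visit for subjects who complete the study on standard-of-care treatment".
- The synopsis and Sections 3.1 and 3.7 also carry an exemption: "For subjects completing Months 4 to 6 on standard of care, a 30-day safety follow-up period is not required".

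Section 3.8.3.1 allows MyCite to be stopped permanently at any time after enrollment and says the sponsor wants to keep following those who stop. Section 3.7.1.3.5 adds that "Month 6/ET visit evaluations are to be completed for any subject withdrawn from the trial at any time", unless consent is fully withdrawn.

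**The concern.** A site needs one answer to the question of who is contacted after the final visit. Section 3.8.3.1 answers everyone. Footnote b and Section 3.7.1.5 answer those who finish on MyCite. Section 5.7.2 sets a requirement from the last dose, and under the restrictive text no scheduled contact delivers it for someone who stopped recently.

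That subject is foreseeable: one who stops MyCite less than 30 days before Month 6 or an ET visit and is on standard of care at that visit. The standard-of-care exemption is sound for a planned Month 3 switcher, but none of the restrictive texts names the late stopper.

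At stake is active detection of new SAEs and IREs in the rest of the post-dose month. Known events remain covered: Section 3.8.3.2 follows adverse events that led to stopping, Section 5.7.2 follows SAEs until they resolve or stabilize, and Section 5.5 has its own 30-day pregnancy notification. Section 5.7.3 does not replace a contact. It covers later events only if someone reports them and the investigator attributes them to MyCite. Section 5.2 sets a 7-month ceiling on adverse event follow-up but does not say who is called.

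**Working it through.** The plan states no figure to reproduce. The check is day arithmetic on the visit schedule.

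**Inputs**

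- Study month: 28 days (Section 3.7.1.3), so Month 3 is Day 84 and Month 6 is 6 × 28 = Day 168.
- Visit window: −3/+2 days (Table 3.7-1), so Month 3 is Day 81 to 86 and Month 6 is Day 165 to 170.
- Required active monitoring: 1 month after last dose (Section 5.7.2), taken as 30 days to match the call.

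**Formulas**

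Let g = (day of Month 6/ET visit) − (day of last MyCite dose), for a subject on standard of care at that visit.

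- Restrictive text: active post-dose detection lasts g days.
- Section 3.8.3.1: it lasts g + 30 days, or g + 27 to g + 33 with the tolerance.

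**Month 6 visit, restrictive text**

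- Coverage is short when the last dose falls after 168 − 30 = Day 138.
- Last dose on Day 139: 168 − 139 = 29 days. Last dose on Day 167: 168 − 167 = 1 day.
- With the visit window the cut-off runs from 165 − 30 = Day 135 to 170 − 30 = Day 140.
- A stop at the Month 5 visit (nominal Day 140) leaves 28 days, or 23 to 33 with both windows.

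**Early termination visit on Day T, restrictive text**

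- The cut-off is Day T − 30: for T = 112, Day 82; for T = 56, Day 26.
- For T = 30 and a first dose on Day 1, g is at most 29. With a visit on Day 30 or earlier, every subject who has already stopped is short.

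**Subjects who are not affected**

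- Planned Month 3 switchers: 168 − 84 = 84 days; least with windows, 165 − 86 = 79 days.
- Subjects taken off MyCite by Day 14 and followed to Month 6: 168 − 14 = 154 days; least, 165 − 14 = 151 days.

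**Same late stopper under Section 3.8.3.1**

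- g = 7: contact 34 to 40 days after the last dose.
- g = 28: contact 55 to 61 days after.
- Any g of 3 or more reaches at least 30 days.

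**Sensitivity to the meaning of 1 month**

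- Read as 28 days, the nominal cut-off moves to 168 − 28 = Day 140.
- If 27 days is accepted, it moves to 168 − 27 = Day 141.
- Later stops remain short in both cases.

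The schedule does not fill the gap. In Table 3.7-1 the only adverse event assessment after Month 6/ET is the follow-up call itself.

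**The case against.** The strongest reply is that the protocol already covers this subject. Someone who stops MyCite outside the Month 3 decision falls under Section 3.8.3.1, which orders a contact, and Section 5.7.2 separately requires monitoring. The restrictive texts say who gets a call but not that nobody else does. The explicit exemption is for completing Months 4 to 6 on standard of care, which hardly describes someone still dosing near Day 139. The Section 3.7 call is timed from the last dose and adds in parentheses that it covers early withdrawals as well as completers. A shortfall therefore needs a site to overlook two sections.

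Much of this stands as a limit on size. Sites that follow 3.8.3.1 or 5.7.2 have no shortfall, and the last-dose timing suggests that 30-day post-dose coverage was the aim. It does not remove the conflict. No precedence is stated, and a site could reasonably go to the schedule table and to the section headed Follow-up. The parenthesis in Section 3.7 sits in a sentence limited at its start to subjects continuing on MyCite. If 3.8.3.1 governs literally, it contradicts the standard-of-care exemption. If 5.7.2 governs, the restrictive schedule has no contact to deliver it.

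A second objection is that the call has a 3-day tolerance either side, so Day 139 is too exact a threshold. That tolerance applies to the timing of the call, not to the Section 5.7.2 window. Allowing it moves the nominal cut-off by 3 days and leaves the gap for later stops.

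A third is that a short cross-reference making 3.8.3.1 and 5.7.2 govern unplanned stoppers would be enough. That would close the gap for them, but the blanket contact in 3.8.3.1 would still conflict with the exemption for planned switchers.

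**Conclusion.** The concern holds. The current text gives incompatible rules for the post-treatment safety contact, and the SAP repeats the restrictive one without resolving it. The textual conflict is certain; the loss of follow-up is conditional on a site following the restrictive text.

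Under that text, subjects who stop less than 30 days before the final visit and end on standard of care lose part of the required month. At a nominal Month 6 visit, a last dose on Days 139 to 167 leaves 29 down to 1 days. At an early termination visit the cut-off is 30 days before that visit. This assumes 1 month means 30 days and that such a subject is not regarded as concluding on MyCite.

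The documents do not allow a count of affected subjects, and it could be zero. The primary endpoint and follow-up of known events are unaffected. The correction should be made because long-term safety is a secondary objective and active detection should not depend on which section a site reads.

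**What to change.** Adopt one rule keyed to the last dose in the synopsis, Sections 3.1, 3.7, 3.7.1.5 and 3.8.3.1 and Table 3.7-1 footnote b, and align SAP Section 3.1:

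- Every dosed subject who is less than 30 days past the last MyCite dose at the Month 6/ET visit receives a safety contact 30 days or more after that dose.
- The standard-of-care exemption applies only to subjects already at least 30 days past their last dose at that visit.

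Two consequences should be stated openly. The rule drops the call that Section 3.8.3.1 now gives planned Month 3 switchers, who are at least 79 days post-dose at Month 6. It also means that any tolerance on the contact falls after day 30 rather than on both sides of it.

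The cost is a wording amendment to the protocol and the SAP description, and at most one extra phone call per affected subject.

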3.8.3.2 Documenting Reasons for Treatment Discontinuation

A subject may discontinue Abilify MyCite for a number of reasons including those listed below:

- Reasons related to AE:

Protocol 031-201-00301

- Subject decides to discontinue because of annoyance or discomfort due to a nonserious AE which is not otherwise determined to be an undue hazard.
- Continuing Abilify MyCite places the subject at undue risk as determined by the investigator (eg, a safety concern that is possibly, probably, or likely related to Abilify MyCite).
 - SAE.
 - Other potentially Abilify MyCite-related safety concerns or AEs.
- Death.
- Reasons unrelated to medical condition (provide detail and review AE history with subject).
- Withdrawal of informed consent (complete written withdrawal of consent form).
- Lost to follow-up.
- Pregnancy (see [Section 5.5](#)).
- Termination of all or part of the trial by the sponsor.

If the subject discontinues Abilify MyCite due to an AE, the investigator, or other trial personnel, will make every effort to follow the event until it has resolved or stabilized.

